#### G2. Interim Monitoring and Early Stopping

As above, we conservatively predict that nicotine treatment will result in a 3% and 10% reduction in FVC and LTS, respectively, relative to the control group. In the spirit of a pilot study, we are unsure of the potency of nicotine in terms of preventing progression or promoting regression of disease, as reflected by the LTS.

Moreover, there is a possibility that nicotine treatment could be ineffective or associated with serious sideeffects in too many patients. As such, the DSMC will continuously monitor the progress of the study and will consider early discontinuation of the trial if nicotine treatment is associated with excess serious adverse events (SAE) (arrhythmias, seizures, syncope, new cancers, death).

#### G3. Analysis Plan

The research data for each Aim will be analyzed at the time of unblinding (year 03). The exception being DSMC data analysis for study related AEs and SAEs, and for analyses relating to performance monitoring, as detailed below.

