# E. Study Design

#### E1. Overview of Design Summary

This will be a prospective, randomized, parallel design with multiple measures, double-blinded, placebocontrolled study conducted on adults with confirmed sarcoidosis (e.g., biopsy proven, or a clinical diagnosis made by sarcoidosis experts) sarcoidosis to determine the effects of transdermal nicotine treatment in patients with active pulmonary disease despite conventional therapies. Patients will be enrolled sequentially and based solely on eligibility. Patients will be randomized in a 1:1 ratio to receive transdermal nicotine 21 mg/daily or an identical-appearing placebo patch. Baseline measurements will be made at the screening and baseline visits on all patients prior to receiving their randomized assigned treatment to a nicotine treatment group (n = 25 patients) and a control group (n = 25 patients) assigned to placebo patch treatment. Nicotine treatment will begin with a 2 week phase in during which the dose of nicotine will be increased weekly towards the highest tolerated dose, using the transdermal drug delivery approach (7 mg patch, 14 mg patch, 21 mg patch). Patients will be maintained on the highest tolerated dose (7-21 mg patch) for the duration of the 24 week treatment protocol. Nicotine treatment will then be deescalated weekly (i.e., 14 mg, 7 mg, and then discontinued).

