#### E3. Study Drug

Description: Sustained release transdermal nicotine (7, 14 and 21 mg daily dose patches) and matching placebo patches will be provided. The nicotine patches and matching control patches will be administered daily according to the manufacturer's recommendations and in compliance with a FDA approved dosing regimen.

Treatment Regimen: To optimize patient compliance and minimize side-effects, nicotine (or matching placebo patch) treatment will be initiated at 7 mg/day and escalated at weekly intervals to 14 mg/day, then 21 mg/day, as tolerated. If intolerance develops, the dose will be reduced to the highest tolerated dose. The dose will be maintained at 21 mg/day (or the highest tolerated dose) for 24 weeks, at which time the dose will be deescalated to 14 mg/day, then 7 mg/day at weekly intervals, after which nicotine treatment will be discontinued.

Method for Assigning Subjects to Treatment Groups: Patients will be randomized to nicotine or placebo patches in a 1:1 ratio. The randomization scheme will be developed by the study statisticians and the scheme allocated through the blinded study subject number. Study drug will be pre-packaged with an assigned study subject number, corresponding to the allocated randomized treatment. Treatment allocations will be blinded to study clinical staff, treating clinicians and patients. Nicotine and replica placebo patches will be randomly designated treatments "A" or "B", and will be distributed by each clinical center. All baseline measurements will be obtained at the screening and baseline visit before allocation of the random assignment

Preparation and Administration of Study Drug: Patients will be instructed to apply a new patch to their skin every day. The site should be clean (e.g., with warm soapy water) and dry at the time of application and only one patch should be placed at a time (old patches must be removed before applying a new one). The backing of the patch is removed to reveal the sticky surface, which is placed on the skin. To avoid local skin irritation, a new site is recommended (e.g., on the upper arm) each day.

Subject Compliance Monitoring: Subject compliance with nicotine will be monitored by history and objectively at regular intervals, as reflected by measuring nicotine and cotinine, a stable nicotine metabolite, as per the Study Schedule of Events (Table 1), described below.

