#### F2. Schedule of Measurements

The schedule for study visits including the assessments and procedures to be performed at each visit is presented in the Schedule of Events (see Table 1). The scheduled study visits should occur at the specified week post-randomization  $\pm$  7 days unless otherwise specified. It is encouraged that study visits be scheduled in the morning, at the same time for each visit, unless extenuating circumstances exist. In addition to scheduled visits, monthly telephone interviews will be conducted by the study site research coordinators to establish/encourage compliance with nicotine (placebo) patches and to screen for adverse events.

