#### F3. Safety and Adverse Events

Safety analyses will be based on treatment received. Safety data, including but not limited to, AEs, serious AEs (SAEs), infections, serious infections, mortality, changes in laboratory assessments, and changes in vital signs. Treatment-emergent AEs will be summarized by treatment group.

All untoward events occurring between the time of obtaining informed consent through Week 34 must be reported as an AE. In keeping with the standards of clinical trials research, the relationship of AEs to nicotine will be classified as "definitely related", "possibly related" or "unrelated", and we will further document the reason for subject dropout, report subjects with multiple adverse events, and track disease exacerbations (requiring escalation of corticosteroid dose or unscheduled healthcare visits).

The severity of AEs will be made using the following general categorical descriptors:

- **Mild:** Awareness of symptoms that are easily tolerated causing minimal discomfort and not interfering with everyday activities.
- Moderate: Sufficient discomfort is present to cause interference with normal activity.
- **Severe**: Extreme distress causing significant impairment of functioning or incapacitation and preventing normal everyday activities.

Based upon our pilot study (11) and previous published reports (33), we expect to see an increase in the frequency of mild side effects with no significant SAEs in the nicotine treatment group compared to placebo controls. These minor side effects tend to abate with continued use of nicotine, and only one subject withdrew from the pilot study due to local skin irritation at the site of the patch. For this reason, we will encourage the subjects to alter the site of the transdermal patch on a daily basis.

There is a potential for a placebo effect with respect to the use of a patch in the nicotine treatment group compared to controls. However, a placebo effect would be expected to influence subjective measures (e.g., dyspnea scores); whereas, objectives measures of lung function or radiographic findings would be effected very little, if at all.

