Subjects will be instructed to call the investigator if their symptoms of sarcoidosis worsen. Based upon the investigator's assessment of the subject's symptoms, functional parameters, and the subjects' history, a clinic visit may be scheduled. If in the investigator's opinion the symptoms of sarcoidosis have worsened sufficiently to require treatment, the investigator will assess the severity and initiate appropriate treatment depending upon the subject's condition. Despite escalation of treatment, the patient will remain enrolled in the study.

Patients will be followed for an additional 4 weeks after nicotine treatment to determine if they required any change in medications, including escalation of therapy for sarcoidosis, and to screen for signs of nicotine dependency or withdrawal. Although nicotine dependency did not occur in the pilot study and is documented to be rare in the setting of transdermal preparations (33), likely due to steady and sustained drug levels (45,46), it remains a potential concern. As such, study subjects demonstrating nicotine dependency or addiction symptoms (e.g., nicotine craving or inability to discontinue nicotine-containing products) one month after discontinuation of the drug will be provided support to engage in a smoking cessation program, which has extensive experienced with nicotine dependency and addiction management (51).

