#### J2. Committees

A Steering Committee (SC) comprised of the PIs from each clinical site, directors of administrative, protocol and clinical research will oversee patient recruitment, the implementation of the research protocols, and the generation of data towards the achievement of the proposed study aims. A Data and Safety Monitoring Board (DSMB) will be appointed to oversee study design, implementation, patient recruitment, interim analyses, adverse events and data management.

х

To cover travel-expenses and			Stu	Study Timeline and Milestones								
other costs relating to	Month	1	2	3	6	9	12	18	24	30	36	48
participation in this project,	IRB approval			х								
subjects will be provided a	Site Visit		х	х			х		х			
stipend of \$50 for each of the 6	SC meeting	х		х	х		х	х	х	х	х	
scheduled protocol-related visits to cover parking/travel expenses.	Subject Recruitment				х	25%	х	50%	75%	100%		
Additional reimbursement for	DSMb	х						х				
travel will be available as needed.	External Advisory Board			x			х		x		x	
J4. Study Timetable	Final Data Analysis										х	

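### Unblinding and final analysis in year 03 (month 36) leave no room for the last patients' 4-week follow-up and week-34 AE window

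*Combined protocol and SAP*

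**What the plan says.** G3 sets one calendar trigger for every Aim, Aim 4 (safety and tolerance) included: "The research data for each Aim will be analyzed at the time of unblinding (year 03". Its only exceptions are the monitoring committee's analyses of AEs and SAEs, and performance monitoring.

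The Study Timeline and Milestones table (J4) shows recruitment at 50%, 75% and 100% under months 18, 24 and 30, and "Final Data Analysis" under month 36. The rows are broken in the text I worked from, so I read these months by column position; they should be confirmed against the original table.

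The patient's schedule comes from four places:

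- E1: "Nicotine treatment will begin with a 2 week phase in during which the dose of nicotine will be increased weekly".
- E3: "The dose will be maintained at 21 mg/day (or the highest tolerated dose) for 24 weeks", followed by a step-down to "14 mg/day, then 7 mg/day at weekly intervals, after which nicotine treatment will be discontinued". Table 1 agrees: escalation in weeks 0-2, stable phase to week 26, de-escalation in weeks 26-28.
- F3, on follow-up: "Patients will be followed for an additional 4 weeks after nicotine treatment".
- F3, on AE reporting: "All untoward events occurring between the time of obtaining informed consent through Week 34 must be reported as an AE".

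The clock starts at randomisation (F2): "The scheduled study visits should occur at the specified week post-randomization", with a window of 7 days either side.

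**The concern.** Recruitment is allowed to run to month 30 and the analysis is set six months later, which is about 26 weeks. A patient's participation lasts 32 weeks by the follow-up text and 34 by the AE text. The last patients therefore cannot have finished when G3 calls for unblinding and analysis.

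What falls late is mainly Aim 4 material. Table 1 marks the dependence assessment only in the follow-up column, and F3 judges dependence one month after the patch is stopped. The follow-up surveys, medication review and AE check sit in the same column. Several of these are self-reported, and F3 itself notes that subjective measures are open to a placebo effect, so it matters that they are complete and collected blind.

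No section makes unblinding conditional on the last patient's last contact or on database lock. The only dated trigger is the calendar year.

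**Working it through.** **Inputs.** Last randomisation at month 30.0 (100% recruitment, J4). Analysis at month 36 (J4), taken as the end of year 03 (G3). 50 patients, 25 per arm (E1). Conversion: 365.25 / 12 / 7 = 4.348 weeks per month.

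**Patient schedule.** 2 + 24 = week 26; + 2 = week 28; both match Table 1. + 4 = week 32 for the end of follow-up, which does not match the week 34 stated for AE reporting. Table 1 gives the follow-up column no week number.

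**Calendar month of each milestone** = month of last randomisation + weeks / 4.348.

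| Milestone | Week | Randomised at 30.0 | Days past month 36 | Randomised at 29.0 |
|---|---|---|---|---|
| End-of-treatment PFT and CT | 26 | 35.98 | fits by under 1 day | 34.98 |
| End of de-escalation | 28 | 36.44 | 13 | 35.44 |
| End of 4-week follow-up | 32 | 37.36 | 41 | 36.36 |
| AE window closes | 34 | 37.82 | 55 | 36.82 |

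The last column is the most generous reading of the labels: last randomisation at the start of month 30, analysis at the end of month 36. De-escalation then fits, but follow-up and the AE window still overrun. To keep month 36, the last randomisation would have to fall by 36 - 32/4.348 = month 28.64 for follow-up, or 36 - 34/4.348 = month 28.18 for the AE window.

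Less generous readings are worse. If 100% is counted at consent, with up to 4 weeks of screening, the four milestones move to 36.90, 37.36, 38.28 and 38.74, and the week-26 measurements miss month 36 as well. Even with randomisation at 30.0, a week-26 visit at the end of its 7-day window falls at 30 + 27/4.348 = 36.21.

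**Patients affected.** The last 25% is 0.25 x 50 = 12.5 patients over months 24 to 30, or 12.5 / 6 = 2.083 per month if accrual is even. Number still open at month 36 = 2.083 x (milestone month - 36):

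- de-escalation: 2.083 x 0.44 = about 0.9
- follow-up: 2.083 x 1.36 = about 2.8 (6% of 50 when rounded to 3)
- AE window: 2.083 x 1.82 = about 3.8 (8% of 50 when rounded to 4)

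**A related mismatch.** The blood-draw text in F4 places the last metabolite sample at week 28, which is month 36.44 for the last patient; Table 1 marks it at week 26. On the F4 timing the batched assay could not be complete by month 36.

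**The case against.** A reader might infer that, followed as written, the plan unblinds the trial while patients are still stepping down or in follow-up, so that late safety data are cut short or collected unblinded. The documents do not support that. F4 keeps the analyses blinded until the study closes. G6 says the blind is normally maintained and allows it to be broken only for emergency treatment. F3 makes AE reporting through week 34 mandatory and says patients will be followed after treatment. Section I keeps the DSMB meeting until after the final subject's assessments. Read together, follow-up is the obligation and year 03 is a planning date; if they collide, a slip of about two months is at least as likely as lost or unblinded data. This part of the objection stands.

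It is also fair that the milestone grid is coarse: it has no column between months 30 and 36, or between 36 and 48, so decimals of a month are only a way to show order and size. The de-escalation overrun depends on a last randomisation at or near month 30.0. Few patients are affected, in a study meant to plan a later trial.

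The inconsistency itself survives. The follow-up and AE overruns remain on every reading of the month labels tried. F4 does not define the close of the study. Section I ties DSMB meetings, not unblinding, to the final assessments. A slipped analysis would itself contradict G3.

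**Conclusion.** The planned dates do not fit together. With recruitment completed at month 30, analysis of every Aim in year 03 leaves no room for the last patients' 4-week follow-up (about month 37.4) or the week-34 AE window (about month 37.8). About 3 to 4 of 50 patients would be affected at month 36. That count assumes even accrual over months 24 to 30 and a last randomisation at month 30.0, neither of which the protocol states.

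On the same assumptions the week-26 FVC and CT data just fit, with no margin for late visits, CT processing or cleaning, and the de-escalation overrun is at most about 13 days. The consequence could be a delayed analysis rather than truncated or unblinded safety data; the documents do not settle which. The defect is a calendar trigger that the trial's own schedule cannot meet for Aim 4. It is modest in size and cheap to correct.

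**What to change.** 1. In G3, replace the year-03 trigger with an event: unblinding and analysis of all Aims take place after the last randomised patient has completed final follow-up and the AE window and the database is locked. Define the close of the study in F4 in the same terms.
2. In the J4 timeline, move the final analysis to no earlier than about month 38 (about 38.7 if recruitment is counted at consent with 4 weeks of screening), plus cleaning time. The month-48 column should not be taken as spare time, because its purpose is not legible in the text available.
3. Reconcile the end of follow-up (28 + 4 = week 32) with the week-34 AE window, and give the follow-up column in Table 1 a week number. Reconcile the week-28 blood draw in F4 with the week-26 mark in Table 1.

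The cost is protocol wording and a delay of a few months in the final analysis, with no additional patients or procedures. An event-based trigger also stays valid if recruitment runs late.

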#### G4. Statistical Methods

The primary study endpoint will determine if nicotine treatment improves an objective measure of lung function that is commonly used in sarcoidosis clinical trials, and is considered to be the "gold standard" clinical endpoint for assessing clinical response in the setting of pulmonary disease activity (59). We will use a longitudinal model, which has certain advantages over the usual ANCOVA (using baseline LTS as covariate) (60). In this analysis both baseline and and post intervention LTS are dependent variables in the longitudinal model (60). Using SAS's Proc Mixed (61), all patients will be included in analysis, whether they are missing either a baseline (unlikely to happen) or a post intervention measurement. Included in the fixed effects model will be race and gender. Interactions with either will only be explored in a sensitivity analysis. With just two measures, we will use a saturated covariance structure (which allows the variances of the baseline and post measures to differ).

For the LTS scores, a longitudinal model, as described in Aim 1, will be used to compare LTS results in each treatment group at baseline and at the completion of the 24 week treatment protocol. Correlation between FVC and LTS: Bivariate plots will be used to describe the relationship between changes in FVC (Aim 1) and LTS (Aim 2). With 25 patients in the nicotine group, where substantial correlation of changes is expected, the standard error of the correlations will be ~0.15 for moderate values.

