The consent form will be reviewed with the prospective study subject or his/her legal representative, and the investigator will be available to answer questions regarding procedures, risks, and alternatives. The principal investigator or his/her entitled designee (as defined on the Delegation List) will obtain written informed consent from each subject or from the subject's legal representative or designee. Consent will be obtained before any protocol-specific procedures are performed. Documentation of the subject's informed consent for and participation in this study will be noted in the subject's medical record. If the subject is enrolled in the ancillary study relating to this protocol, a sub study-specific consent must also be used. The subject or his/her legal representative must be provided with a copy of the consent form for the main study and a copy of any separate consent form for the sub study (if applicable).

Randomization Method and Blinding: Patients will be randomized to nicotine or placebo in a 1:1 ratio. Randomization will be within each site (balanced by site) and use permuted blocks of varying size (2,4,6). The randomization scheme will be developed by the study statisticians and the scheme allocated through the blinded study subject number. Study drug will be pre-packaged with an assigned study subject number, corresponding to the allocated randomized treatment. All baseline measurements will be obtained at the screening and baseline visit before allocation of the random assignment. Identically labeled nicotine and placebo patches will be randomly designated treatments "A" or "B", and will be distributed by each clinical center.

*Risks and Benefits:* Nicotine intolerance rates are very low, even at doses 2-fold greater than the maximum dose used in this study (48). Common (>10%) minor side effects observed in our pilot study (11), and reported elsewhere (33), includes local skin irritation, headaches, nightmares, sleep disturbances. We are aware of the potential for serious adverse events, particularly cardiac arrhythmias (49) and seizures (50) in patients with underlying heart or central nervous system disease, respectively, and will exclude patients with these risk factors from enrollment in this study.

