#### F4. Study Outcome Measurements and Ascertainment

The primary endpoint of the study will be the change in FVC, measured before and after treatment with nicotine or placebo for a total of 24 weeks.

The secondary clinical endpoint of major interest will be the change in total burden of lung disease, as reflected by the computer-generated CT image analysis or changes in lung function. Data files will be deidentified and thereby blinded to the investigative team. Moreover, the computer-generated Lung Texture Score (LTS) ascertained from these analyses are objective, highly reproducible, and strongly correlate with standard physiological (PFT) measures (32).

Other secondary endpoints will determine if changes in LTS correlate with changes in simultaneous PFT measures or measures of the rate of nicotine metabolism, as reflected by the ratio of 3-hydroxycotinine to cotinine in serum samples. Finally, the effects of nicotine treatment on disease-related symptoms will be determined by comparing the results of surveys (SAT, SGRQ, FAS) conducted at regular intervals during the study protocol. Again, these analyses will remain blinded to treatment allocation until the close and un-blinding of the study.

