## G. Statistical Plan

#### G1. Sample Size Determination and Power

Depending on the clinical efficacy of nicotine compared to another immune modulating agent (infliximab), we expect to see up to 3% improvement in FVC in the nicotine treatment group based upon a comparable study design in patients with active pulmonary sarcoidosis (27). With the expected 25 patients per group and average change variance at a minimum of 3% for FVC, the precision of a comparison of means is roughly adequate for planning, but is insufficient for achieving significance unless the nicotine effect on FVC is large (e.g., >5%) as compared to controls. We will report *p*-values for these as secondary outcomes, and derive meaning only if our primary outcome (FVC) shows significance, i.e. we will use some of the logic of gatekeeping hypothesis testing (57). Assuming 5-10% variance (standard deviation) between consecutive FVC measurements, and a 3% change in FVC with treatment the estimated study size would range from 44-178 in each arm of the subsequent Phase II trial.

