#### G5. Missing Outcome Data

Assuming a 10% dropout before follow-up, complete data will be obtained from ~22 subjects in each arm of the study. The missing at random (MAR) assumption will be our primary adjustment for potential missing data bias (62,63). Sensitivity analyses will confirm the main findings as recommended by the special NAS panel on missing data in clinical trials (63).

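### The longitudinal model in G4 does not name site, although randomisation is blocked within two sites; its primary-endpoint paragraph also prints LTS where FVC is meant

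*Combined protocol and SAP*

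**What the plan says.** Randomisation (E2, Randomization Method and Blinding): "Randomization will be within each site (balanced by site) and use permuted blocks of varying size (2,4,6"). J1 names two clinical centres and describes their sarcoidosis populations as demographically different. Table 2 puts the African American share at 45% in one and 26% in the other.

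Analysis (G4): both measurements of the outcome are dependent variables in a mixed model with a saturated covariance. On covariates it states: "Included in the fixed effects model will be race and gender". Interactions with those two are left to a sensitivity analysis. Site is not mentioned in G4 or in any other analysis section.

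Outcome named in the model: F4 states "The primary endpoint of the study will be the change in FVC", and Aim 1 in section C is also about FVC. The first paragraph of G4 opens with the primary, lung-function endpoint but then reads: "In this analysis both baseline and and post intervention LTS are dependent variables in the longitudinal model (60"). The comparison with ANCOVA in that paragraph also refers to baseline LTS. The second paragraph turns to LTS separately: "For the LTS scores, a longitudinal model, as described in Aim 1, will be used".

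Planning figures (G1 and G5): "Assuming 5-10% variance (standard deviation) between consecutive FVC measurements, and a 3% change in FVC with treatment"; 25 patients per arm; and "complete data will be obtained from ~22 subjects in each arm of the study". G1 will "derive meaning only if our primary outcome (FVC) shows significance", so the FVC test is the gate for interpreting the other outcomes.

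**The concern.** Blocking within site forces the arms to be balanced on site. The precision this buys is realised only if the analysis also accounts for site. If mean FVC change differs between centres and the model ignores it, that difference stays in the residual variance. The standard error is then too large for the design actually used, the test rejects less often than its nominal level, and power is given up. The treatment estimate is not biased and type I error is not inflated.

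Precision is what this pilot is for. Aim 1 is to size a later trial, and G1 itself describes the precision as only roughly sufficient for planning.

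A site main effect would not be enough. With baseline and post-treatment values both on the left-hand side, a main effect shifts both by the same amount and cancels in the change. Only site-by-time lets the mean change differ by site.

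Separately, no model in G4 names FVC as its dependent variable, although FVC is the primary endpoint and the gate.

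**Working it through.** **Inputs from the documents.** Two sites (J1); permuted blocks of 2, 4 and 6 within site (E2); 25 per arm (E1); about 22 completers per arm (G5); FVC effect 3%, SD of change 5–10% (G1).

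**Assumptions.** Two-sided 5% test (G1 gives 0.05 for LTS only, and no sidedness); two sites of 25; total SD of change held fixed; share *s* of the change variance due to site set at 0, 5, 10 and 20%, since the documents give none.

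**The plan's own figure.** n per arm = 2(1.960 + 0.842)² SD²/δ². SD 5: 2 × 7.849 × 25/9 = 43.6, so 44 (plan: 44). SD 10: 174.4, so 175 (plan: 178, within 2%). The match is at 80% power, which G1 does not state for FVC. These inputs are therefore the plan's.

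**Closed form, SD 5%, 25 per arm.** Standard error used when site is ignored: 5 × √(2/25) = 1.414. True standard error under within-site balance: 1.414 × √(1 − s).

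- Type I error without site = 2[1 − Φ(1.96/√(1 − s))]: 5.0%, 4.4%, 3.9%, 2.8% for s = 0, 5, 10, 20%.
- Power without site = Φ((3 − 1.96 × 1.414)/(1.414√(1 − s))): 56–57% throughout.
- Power with site = Φ(3/(1.414√(1 − s)) − 1.96): 56%, 59%, 61%, 66%.
- 95% half-width with site = 1.96 × 1.414 × √(1 − s): 2.77, 2.70, 2.63, 2.48 points; without site it is 2.77.

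**Simulation of change, t-based, 10,000 runs per setting** (Monte Carlo error about 0.5 points for power, 0.2 for type I error). Each cell: without site / with site, in %.

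| Site share | Type I error, SD 5%, 25 per arm | Power, SD 5%, 25 per arm | Power, SD 5%, 22 per arm | Power, SD 10%, 25 per arm |
|---|---|---|---|---|
| 0 | 5.2 / 5.2 | 55.6 / 55.5 | 49.2 / 49.1 | 17.5 / 17.5 |
| 5% | 4.6 / 5.3 | 53.4 / 55.5 | 48.6 / 50.7 | 17.6 / 18.9 |
| 10% | 3.9 / 5.0 | 53.8 / 58.4 | 49.7 / 53.8 | 16.5 / 18.9 |
| 20% | 2.8 / 4.8 | 54.7 / 63.9 | 49.2 / 58.4 | 15.1 / 21.8 |

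**Simulation of the two-measure model** (saturated covariance, 25 per arm, SD of change 5%, baseline SD 15% assumed, 4,000 runs). Power in %:

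| Site share | No site | Site main effect only | Site and site-by-time |
|---|---|---|---|
| 5% | 55.2 | 54.7 | 56.9 |
| 10% | 54.1 | 53.6 | 58.1 |
| 20% | 55.5 | 55.1 | 64.2 |

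Type I error at the 20% share was 2.7%, 2.6% and 4.4%. The main effect alone recovers nothing.

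**What each share implies.** With two equal sites the difference in mean change is g = 2 × SD × √s. At SD 5%: 2.2, 3.2 and 4.5 points for 5, 10 and 20%. At SD 10%: 4.5, 6.3 and 8.9 points.

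**Wording.** Section C (Aim 1), F4 and the gate in G1 all make FVC primary. The second paragraph of G4 handles LTS by pointing back to the Aim 1 model. The first paragraph can therefore only be meant for FVC, and no figure depends on the slip.

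**The case against.** The strongest case is about size. A 10% share needs a between-site difference in mean FVC change of 3.2 points at SD 5%, about the whole drug effect, and a 20% share needs 4.5 points. Section C says effective treatments typically move FVC by less than 5%. The outcome is within-patient change, so constant site offsets cancel, and spirometry follows ATS guidelines. At a 5% share the gain is about 2 points of power. G1 already accepts that significance is unlikely unless the effect is large, and adding site alters none of the printed figures. This stands: the upper rows are outer bounds, and a few points is the realistic gain.

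The G4 sentence is also not a full model statement, since treatment and time are not listed either. The fair reading is that site is not named, not that it was deliberately excluded. But treatment and time are inherent in the comparison, whereas site is a choice, and silence leaves that choice open until after unblinding.

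Race might stand in for site, since race mix differs by centre. As a main effect it does not: with the Table 2 race mix and a 20% share, power was 55.6% with no covariate, 55.2% with race and 64.8% with site and site-by-time. The same limitation applies to the race and gender main effects in the plan. That is a fair observation, but those are not stratification factors.

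The LTS slip is clerical and adds no weight to the site point.

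**Conclusion.** The concern holds. The trial randomises within site and the plan does not analyse by site. The consequence is lost precision and a conservative test, with no bias and no excess false positives. At SD 5% and 25 per arm, including site and site-by-time raises power for a 3% effect by about 2 points at a 5% site share, 5 at 10% and 9 at 20%, and by nothing at zero. The shares, the equal site sizes and the two-sided 5% level are assumptions; given the site differences they imply, the lower end is the more credible. The change is still worth making before unblinding because it costs almost nothing and settles the model for the endpoint that gates the rest. The LTS/FVC wording needs correcting for clarity only.

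**What to change.** - In G4, add site and site-by-time as fixed effects to the FVC model and to the LTS model.
- In the first paragraph of G4, replace LTS with FVC in both places, and state that the same model is then applied to LTS.
- Race-by-time and gender-by-time terms are optional and not part of this change.

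Cost: a few lines of SAP wording and about two degrees of freedom. Site is already recorded, so no new data are needed. At a site share of zero the power is unchanged (55.6% against 55.5%).
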